#### 6.1.7 Day 56 (± 2 days) – Follow-up Visit

At Day 56, all subjects will return to the clinic for the following procedures:

- Vital sign collection (heart rate, blood pressure, respiratory rate, and oral temperature).
- Interval history to query for any MAEs, SNMCs, or SAEs occurring since the last trial visit, and any concomitant medications taken for these events. A directed physical examination may be performed at the investigator's discretion to evaluate any AEs.
- Schedule the Day 90 telephone contact and the Day 182 in-clinic visit.

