Data concerning all classes of adverse events will be collected at scheduled visits from the time informed consent is obtained through 21 days post-injection. Note: The 21 day post vaccination all adverse event profile will include all unsolicited AEs reported from test article receipt until the day preceding the rescue dose, ie, events with onset dates between days 0 to 20 for subjects who receive the rescue dose as scheduled on day 21. Rules for defining the dataset in subjects who receive the rescue dose before or after day 21, or no rescue dose, are detailed in the statistical analysis plan. After these specified days, data concerning MAEs, SNMCs, and SAEs will be collected (see Sections 8.1.5 and 8.2 for details of these AEs), as well as additional information regarding outcomes/resolutions of AEs reported prior that had no stop date recorded. In addition to the scheduled visits, subjects will be instructed to notify the investigator and/or return to the clinic if any severe AE (solicited or otherwise) or event fulfilling the definition of an SAE occurs at any time following vaccination. If at a scheduled or unscheduled visit, symptoms are presented that would require a physical exam to adequately assess potential AEs, the exam should be performed and vital signs collected. Adverse events will be recorded as observed by the investigator, designated personnel, or as provided by the subject on the diary card or during the in-person visit. Full details of the AE (ie, nature, date of onset, and recovery, as well as an assessment of severity, relationship to trial treatment [unsolicited events only], seriousness, treatment, and outcome) will be recorded in the source documentation and captured in the eCRF, and will generally require the investigator(s) causality assessment, except as discussed below.

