8.1.2 Unsolicited Adverse Events

Unsolicited adverse events are defined as any adverse events occurring within the 7-day window following vaccination and not specifically solicited in the diary, or any solicited event that occurs outside the 7-day diary solicitation period. The number (percentage) of subjects with unsolicited AEs will be summarized by MedDRA SOC and PT.

The following summaries of unsolicited AEs will be presented for all subjects in the Safety Population as part of the primary analysis of safety:

- Overall summary of unsolicited AEs by treatment group (Days 0 21).
- A summary by severity (mild, moderate, or severe), MedDRA SOC, PT, and treatment group (Days 0 21).
- A summary by relationship (possibly, probably, definitely, or unlikely/unrelated) to test article, MedDRA SOC, PT, and treatment group (Days 0 21).

• A summary of severe related (possibly, probably, definitely) AEs, MedDRA SOC, PT, and treatment group (Days 0 - 21).

The 'twenty-one (21) days post-vaccination' dataset is intended to capture short and moderate term unsolicited AEs occurring in the approximate 3 weeks after the investigational product (or comparator) exposure and not attributable to the rescue treatment." The dataset will contain the following unsolicited AEs:

- In subjects who receive the rescue dose on Day 21, all unsolicited AEs with start dates on Days 0 to 20.
- In subjects who receive the rescue dose prior to Day 21, all unsolicited AEs with start dates on Days 0 to the day of rescue dose -1.
- In subjects who receive the rescue dose on Days 22 or 23, all unsolicited AEs with start dates on Days 0 to the day of rescue dose -1.
- In subjects who receive the rescue dose after Day 23, or who do not receive the rescue dose, all unsolicited AEs with start dates on Days 0 to 22.

In addition to the above summaries, the final analysis will also include the following summaries of unsolicited AEs:

- An overall summary of unsolicited AEs (Days 0 364).
- A summary by severity (normal, mild, moderate, or severe), MedDRA SOC, PT, treatment group (Days 0 364).
- A summary by relationship (possibly, probably, definitely, or unlikely/unrelated) to test article, MedDRA SOC, PT, treatment group (Days 0 364).
- A summary of severe related AEs, SAEs, MAEs, and SNMCs, by MedDRA SOC, PT, and treatment group will be prepared for Days 0 – 364, if any such events are reported after Day 21.

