Appendix 1 – TNIV-E-101 TRIAL PROCEDURES SCHEDULE

Note: Procedures shaded in grey are performed via scripted telephone call.

^[1] Vital signs to be captured pre-vaccination and between 30 to 60 minutes post-vaccination.

^[2] Includes assessments for hematology (complete blood count [CBC] with hemoglobin, hematocrit, red blood cell [RBC] count, platelet count, and white blood cell [WBC] count with differential) and serum chemistry (alanine aminotransferase [ALT], aspartate aminotransferase [AST], total bilirubin, alkaline phosphatase, creatinine, and blood urea nitrogen [BUN]).

^[3] Subjects will be asked to report any grade 3 solicited or unsolicited adverse event or SAE experienced since the last visit and may be asked to return to the clinic for an unscheduled visit to evaluate the event(s) at the Investigator's discretion.

^[4] All adverse events and concomitant medications taken will be collected through Day 21; thereafter only MAEs, SAEs, and SNMCs and medications taken for these events will be collected.

^[5] The subject diary will be reviewed by the investigator and collected at the Day 7 visit (Stage 1 subjects ONLY) or Day 21 visit (Stage 2 subjects ONLY).

^[6] On Day 21, all Group A and B subjects will be administered a rescue injection with a licensed influenza vaccine, and all Group C subjects will be administered an injection of saline placebo to maintain trial blind. Subjects should be free of acute illness (defined as the presence of a moderate or severe illness with or without fever, or an oral temperature $\geq 38.0^{\circ}$ C) in order to receive the second vaccination. Subjects presenting with an acute illness on Day 21 may return to the study site within the next 7 days to receive their 2nd vaccination. If a subject has experienced any AEs/SAE between study Days 0 and 21, then Day 21 vaccination may be administered or delayed for up to 7 days based on the Investigator's discretion.

^[7] If needed, a physical examination may be performed, based on the investigator's discretion.

^[8] All Stage 1 subjects will be required to complete a Day 7 in-clinic visit to present their subject diaries, whereas Stage 2 subjects will be required to complete a safety telephone call.

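### The Days 0–364 tables of all unsolicited AEs in SAP 8.1.2 run 343 days past full AE collection, so their percentages are lower bounds and need restricting or relabelling

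*SAP*

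**What the plan says.** SAP 8.1.2 first sets out summaries of unsolicited AEs for the 21-day period, with rules that close each subject's dataset around the rescue injection. It continues: "In addition to the above summaries, the final analysis will also include the following summaries of unsolicited AEs". Three of the items that follow are labelled Days 0–364 and name no event class:

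- "An overall summary of unsolicited AEs";
- "A summary by severity (normal, mild, moderate, or severe), MedDRA SOC, PT, treatment group";
- a matching table by relationship to test article.

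A fourth item, on severe related AEs, SAEs, MAEs and SNMCs, is to be prepared only if such events are reported after Day 21. SAP 8.2 adds that MAEs and SNMCs are counted in the overall AE summary.

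The collection rule is narrower than those table labels. SAP Appendix 1, footnote 4 (and the same footnote in the protocol) says of the time after Day 21: "thereafter only MAEs, SAEs, and SNMCs and medications taken for these events will be collected". Protocol 8.1 agrees: "After these specified days, data concerning MAEs, SNMCs, and SAEs will be collected", together with outcomes of earlier AEs still open. The Day 56 visit is typical of the later contacts: "Interval history to query for any MAEs, SNMCs, or SAEs occurring since the last trial visit".

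**The concern.** A table titled as unsolicited AEs for Days 0–364 invites the reader to take its percentages as a one-year AE profile. For most of that year, ordinary AEs that are neither medically attended, serious nor a significant new condition are not asked about. The tables add a complete record for three weeks to a restricted record for the rest of the year, and nothing in 8.1.2 tells the reader so.

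At stake is the reading of final safety tables for a first-in-human adjuvanted vaccine. The overall percentage would look like an annual incidence when it is not. The severity and relationship tables would describe a mixture of two collection rules, which matches neither the 21-day nor the one-year safety endpoint.

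**Working it through.** The plan gives no figure for this gap, so there is none to reproduce.

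**1. Length of restricted collection.** Inputs: end of full AE collection, Day 21 (Appendix 1, footnote 4); end of the table window, Day 364 (SAP 8.1.2).

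- 364 − 21 = 343 days.
- 343 / 364 = 94.2% of the labelled window.
- With the ±2-day window on the Day 21 visit: 364 − 23 = 341 to 364 − 19 = 345 days.

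**2. Collection set against tabulation.**

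| Period | Systematically collected | Counted in the three tables |
|---|---|---|
| Through Day 21 | all AEs | all unsolicited AEs |
| After Day 21, to Day 364 | MAEs, SAEs, SNMCs | labelled as all unsolicited AEs |

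Protocol 6.1.7 to 6.1.11 (Days 56, 90, 182, 273 and 364) confirm the second row: every contact asks only for those three classes.

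**3. Tabulation set against endpoints.** The primary safety endpoint (Protocol 3.2.1, SAP 2.2.1) covers all AEs through 21 days and MAEs, SAEs and SNMCs through one year. There is no one-year endpoint for all AEs. SAP Section 13 records no change from the protocol's analyses.

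**4. Direction.** A subject with any recorded unsolicited AE has had one, but a subject with only an unattended mild AE after Day 21 may have no record. The number recorded therefore cannot exceed the number affected, and the overall percentage is a lower bound. The loss falls mainly on mild and moderate unattended events, so the mix moves toward attended and serious ones. A single severity row need not itself be a lower bound: SAP 8.1 counts repeated occurrences of an event at the worst grade, so a missed later moderate occurrence can leave a subject in the mild row.

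**5. Size.** The documents give no AE rate for this trial and no share of AEs that are MAE, SAE or SNMC, so no corrected percentage can be computed. The following shows only how much depends on those unknowns; every input is an assumption. Suppose 20% of subjects have an unsolicited AE in the 22 days from Day 0 to Day 21. Let the later daily hazard be a fraction r of the early one, and let a share f of later AEs be MAE, SAE or SNMC.

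- Early daily hazard λ = −ln(1 − 0.20) / 22 = 0.01014.
- Tabulated = 1 − exp[−λ(22 + r·f·343)].
- Actual = 1 − exp[−λ(22 + r·343)].

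| r | f | Tabulated | Actual | Difference (unrounded inputs) |
|---|---|---|---|---|
| 0.1 | 0.3 | 0.279 | 0.435 | 0.156 |
| 0.1 | 0.7 | 0.373 | 0.435 | 0.062 |
| 0.5 | 0.3 | 0.525 | 0.860 | 0.334 |
| 0.5 | 0.7 | 0.763 | 0.860 | 0.096 |

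Across these assumptions the shortfall is about 6 to 33 percentage points. With f = 1 it is zero. That spread is why no single figure should be quoted.

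**The case against.** The best defence is that these are supplementary descriptive counts of what was recorded, not estimates of one-year risk. The collection rule is disclosed in the SAP's own appendix. SAP 8.2 says that MAEs and SNMCs are part of the overall AE summary, and the fourth item in 8.1.2 shows that the authors had the later period in mind. The summaries that match the endpoints are already planned: the 21-day tables, MAEs and SNMCs for Days 0–364 (SAP 8.2), and an SAE listing for Days 0–364 (SAP 8.3). All three groups follow the same collection rule.

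Severe events are also less exposed than the rest. Protocol 6.2 and 8.1 ask subjects to report severe AEs at any time, and the grading table expects Grade 3 events generally to need medical attention.

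A blunt restriction would also lose information. For a subject rescued on Day 21, the 21-day dataset ends at Day 20. AEs during monitoring after the Day 21 injection (Protocol 6.1.6), and Day 21 laboratory changes that must be reported as AEs (Protocol 8.1.4) if their onset is dated to that sample, fall outside it. Moving them to a listing would remove them from every percentage table.

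All of this stands, and it limits the point. It does not remove the mismatch: a rule in an appendix footnote is not carried into the titles or definitions of the three tables. The last argument bears on the form of the fix, not on the need for one.

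**Conclusion.** The point holds as a mismatch between collection and labelling. For 343 of the 364 days, the three tables can systematically contain only MAEs, SAEs and SNMCs. Their overall percentages are lower bounds on one-year unsolicited AE incidence, and their severity and relationship mix is tilted toward medically attended and serious events. This rests only on the collection rules and table definitions in the two documents; the illustration above is not part of the conclusion.

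Three stronger readings are tempting and should not be drawn:

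- A reader might infer that the tables are simply wrong. Recorded events are not miscounted; the label claims more than was observed.
- A reader might divide the labelled window by the period of full collection and infer an understatement of that proportion. The tables report percentages of subjects, not rates per unit of time. The inference also needs a constant hazard for a year, which nothing in the documents supports, and it ignores the later MAEs, SAEs and SNMCs that the tables do count.
- A reader might infer that the trial's safety conclusions are compromised. The primary safety endpoints and the 21-day tables are defined separately and are unaffected.

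This is a reporting defect that should be corrected before the final analysis.

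**What to change.** In SAP 8.1.2:

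1. Base the Days 0–364 overall, severity and relationship percentages on events designated MAE, SAE or SNMC. This is the stated one-year endpoint, and the eCRF already has the fields.
2. Report all unsolicited AEs only for the period of full collection, using the existing 21-day dataset.
3. Give a separately labelled count by group of other AEs recorded after a subject's 21-day dataset closes: onset on Day 21, Day 21 laboratory AEs, AEs after the second injection, and later severe AEs reported spontaneously. A listing alone is not enough. The separate label also matters because the second injection is licensed vaccine in Groups A and B and saline in Group C.
4. If a cumulative table is kept, split it by period and title it *all unsolicited AEs through Day 21; MAE/SAE/SNMC thereafter*.

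The cost is SAP wording, a filter in three table programs and one added count. No new data are needed. The downside is that no single all-AE percentage will span the whole trial.

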#### Follow-up Telephone Contact/In-clinic Visits

Safety follow-up visits will be performed by scripted telephone contact on Day 3 to query for any grade 3 solicited or unsolicited event and/or SAE experienced since the last visit or telephone contact, and any concomitant medications taken for these events. Subjects who report a grade 3 event and/or SAE may be asked to return to the clinic for an unscheduled visit at the investigator's discretion. Subjects in Stage 1 of the trial will complete a Day 7 (+1 day) in-clinic visit to return their diaries, provide vital signs, report any AEs they experienced since their last visit, and schedule their next Day 21 ( $\pm$  2 days) in-clinic visit. Subjects will Stage 2 will complete a Day 7 ( $\pm$ 1 day) telephone call with the trial staff and will return their diaries on their next Day 21 (± 2 days) in-clinic visit. On their Day 21 visit, all subjects will be queried for any AEs, MAEs, SNMCs, and SAEs occurring since the last trial visit, and any concomitant medications taken. In addition, the following procedures will be performed on Day 21 for all subjects: vital sign collection and collection of blood samples for immunogenicity testing (eg, HAI/MN titers; 20 mL) and clinical laboratory safety assessments of hematology and serum chemistry parameters (10 mL). A rescue injection with a licensed seasonal influenza vaccine will be administered to all subjects that received Tri-NIV on Day 0, according to the manufacturer's instruction, whereas all subjects who received Fluzone HD on Day 0 will be given an injection of sterile saline placebo to maintain trial blind. Administration should be performed on the dominant deltoid. Note: if only the non-dominant deltoid is available for injection, it is acceptable to administer the trial treatment in the non-dominant deltoid. Subjects should be free of acute illness (defined as the presence of a moderate or severe illness with or without fever, or an oral temperature  $\geq 38.0^{\circ}$ C) in order to receive the second vaccination. Subjects presenting with an acute illness on Day 21 may return to the study site within the next 7 days to receive their 2nd vaccination. If a subject has experienced any AEs/SAE between study Days 0 and 21, then Day 21 vaccination may be administered or delayed for up to 7 days based on the Investigator's discretion. Subjects will be monitored in the clinic for 30 to 60 minutes following injection with the trial treatment for the occurrence of any AEs and for the evaluation of post-vaccination vital signs.

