# **10.4 Analyses Addressing Protocol Objectives**

#### 10.4.1 Analyses of Primary Objectives

#### 10.4.1.1 Safety

Safety analysis will be descriptive and based on the safety population, defined as all subjects who received a dose of trial treatment. Safety will be summarized overall and by individual treatment arms based on solicited short-term reactogenicity post-injection on Day 0, 21-day all AE profile by MedDRA preferred term, and 1-year MAE, SAE, and SNMC profiles post-injection on Day 0. Note: The 21 day post vaccination all adverse event profile will include all unsolicited AEs reported from test article receipt until the day preceding the rescue dose, ie, events with onset dates between days 0 to 20 for subjects who receive the rescue dose as scheduled on day 21. Rules for defining the dataset in subjects who receive the rescue dose before or after day 21, or no rescue dose, are detailed in the statistical analysis plan. All AEs, MAEs, SAEs, and SNMCs will be tabulated by severity, related (possibly, probably, or definitely vs. non-related per investigator assessment), and severe and related. The number and percentage (with 95% CI) of subjects in each treatment group with a given term will be summarized. Clinical laboratory data will be summarized by means and 95% confidence interval, minima and maxima, at Day 0 and Day 21 in each treatment group, as well as means and 95% confidence interval of change from baseline at Day 21. Changes from baseline will also be summarized at Day 21 for each treatment group in terms of the proportion of subjects with no change in toxicity grade versus proportions with one, two, or three grade changes. A listing and narratives of SAEs will also be produced.

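### The condition on the SAP 8.1.2 Days 0-364 severe-and-related table can leave an event on the day of the second injection out of the joint count

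*SAP*

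**What the plan says.** SAP 8.1.2 lists, for the primary safety analysis, "A summary of severe related (possibly, probably, definitely) AEs, MedDRA SOC, PT, and treatment group (Days 0 - 21", with no condition attached. The dataset rule below that list sets which onsets count. For an injection on schedule it reads "In subjects who receive the rescue dose on Day 21, all unsolicited AEs with start dates on Days 0 to 20". For an early one it begins "In subjects who receive the rescue dose prior to Day 21, all unsolicited AEs with start dates on Days 0 to the day of rescue", and for one slightly late "In subjects who receive the rescue dose on Days 22 or 23, all unsolicited AEs with start dates on Days 0 to the day"; in both cases the last day included is the day before the dose. If the dose comes after Day 23 or is not given, onsets through Day 22 count.

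For the final analysis, SAP 8.1.2 adds one more severe-and-related summary: "A summary of severe related AEs, SAEs, MAEs, and SNMCs, by MedDRA SOC, PT, and treatment group will be prepared for Days 0" through 364, but only "if any such events are reported after Day 21". The other Days 0-364 summaries in that list (overall, by severity, by relationship) carry no condition.

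Protocol 10.4.1.1 states: "All AEs, MAEs, SAEs, and SNMCs will be tabulated by severity, related", and then the combination of severe and related. It attaches no condition. SAP Section 13, which should record changes from the protocol's analyses, reads NA.

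On the second injection, the protocol synopsis (Follow-up Telephone Contact/In-clinic Visits) says: "Subjects will be monitored in the clinic for 30 to 60 minutes following injection with the trial treatment for the occurrence of any AEs". Under the procedures schedule, all adverse events are collected through Day 21, and only MAEs, SAEs and SNMCs after that.

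**The concern.** The two tables are bounded by different clocks. The first is cut by onset date relative to the injection. The second is switched on by report date relative to Day 21. When the injection is given on or before Day 21, the injection day lies outside the first bound and does not meet the second.

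That day is one on which the plan actively observes subjects, so an event that starts and is reported the same day is foreseeable. If it were rated severe and related and nothing else triggered the second table, the reported severe-and-related count could be zero while the database held one. The separate severity and relationship tables would not settle the matter. SAP 8.1 counts each subject once per event, using the most severe occurrence in one table and the most related in the other, so the joint classification cannot be read off the two margins.

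**Working it through.** The plan states no figure on this point, so the check is of the rules themselves.

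**Inputs.** The last onset day in the 21-day dataset (SAP 8.1.2) is r − 1 for a second injection on day r ≤ 23, and Day 22 for a later or omitted one. The trigger for the Days 0-364 table is a report after Day 21. The visit window is Day 21 ± 2 (Protocol 6.1.6), with a delay of up to 7 days allowed. I take the rescue dose to mean the second injection in all three groups, since Table 1 places the Group C placebo in the rescue column.

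**Test case.** A severe related event with onset and report both on day r.

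| Second injection | Last onset in first table | Event in first table? | Report triggers second table? |
|---|---|---|---|
| Day 19 | Day 18 | no | no |
| Day 20 | Day 19 | no | no |
| Day 21 | Day 20 | no | no |
| Day 22 | Day 21 | no | yes |
| Day 23 | Day 22 | no | yes |
| Days 24-28 | Day 22 | no | yes |

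The gap therefore covers the scheduled day and the early half of the window. It closes for later injections, and also for a reaction on Day 19, 20 or 21 that is reported only after Day 21.

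**How much depends on the meaning of *such events*.** Suppose each of 330 subjects independently has probability p of a qualifying report after Day 21. The chance that the table is not triggered is (1 − p)^330. The documents give no value of p for this trial, so those below are assumptions.

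- Only severe related events qualify: p = 0.1%, 0.2%, 0.4% and 0.7% give 0.72, 0.52, 0.27 and 0.10. The last two rates match the placebo and active figures for severe related events in the Phase 3 RSV F trial in Protocol 1.9. That trial used a different, unadjuvanted antigen, and its figures are not restricted to reports after Day 21, so they serve only as orientation.
- Any SAE, MAE or SNMC qualifies: p = 20% gives about 1 × 10⁻³². The table is then practically certain, and it would include the injection-day event.

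These are chances that the table is not made. They are not chances that an event is missed.

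**The case against.** The strongest reply is that the condition is an ordinary rule against repeating a table when nothing new has occurred, and that *such events* can be read as any SAE, MAE or SNMC, the classes still collected after Day 21. On that reading the table will be made and nothing is lost. This stands as a possible reading, but the sentence does not settle whether severe and related qualifies all four classes. On the broad reading the condition does no work, so removing it costs nothing.

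Second, relatedness is rated to the test article (Protocol 8.5), and the category for unrelated or unlikely events covers those readily explained by other treatments. A reaction minutes after a licensed vaccine may be rated unrelated, and it would then be absent from any severe-and-related table. This stands as a limit. It does not remove the case: the synopsis calls the Day 21 injection trial treatment, and SAP 12.5 counts a missing relationship as related.

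Third, keeping the injection day out of the first table is deliberate, because that dataset is meant to exclude effects of the rescue treatment. This is correct. The difficulty is that the second table does not reliably pick up what the first leaves out.

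Fourth, the first table is labelled Days 0 - 21, which read literally would include Day 21. The dataset rule beneath the label and Protocol 10.4.1.1 both end the profile the day before the dose, so the label does not close the gap.

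**Conclusion.** The point holds in a narrow form. Reading *such events* as severe related events, one that starts and is reported on an injection day of 19, 20 or 21 can be absent from both severe-and-related tables, contrary to the unconditional commitment in Protocol 10.4.1.1. This requires that the event be rated related to the test article and that no other such event be reported after Day 21. The joint probability is small, and the documents give no rate from which to compute it.

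Three stronger conclusions that a reader might infer are not supported:

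- That the event would vanish from the report. The Days 0-364 severity and relationship tables are unconditional, SAP 12.5 puts all eCRF data in listings, and SAEs also receive narratives. Only the joint count is at risk.
- That the chance of the Days 0-364 table not being made measures the harm. Where no severe related event occurs on the injection day, omitting the table hides no such event.
- That Day 21 is the only look at a licensed vaccine given after Tri-NIV. MAEs, SAEs and SNMCs are queried at Days 56, 90, 182, 273 and 364.

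This is a minor correction to a reporting rule.

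**What to change.** In the last bullet of SAP 8.1.2, delete the condition on reports after Day 21, so that the Days 0-364 severe-and-related summary is always produced, as Protocol 10.4.1.1 states. If a condition is kept, trigger the table on any such event with onset outside the 21-day dataset, not on report date, and say which event classes *such events* covers. While editing, reconcile the Days 0 - 21 label with the dataset rule. A sub-row for onsets on or after the second injection is optional; it would keep those events distinct from the 21-day profile.

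The cost is one clause removed and one table that may have few rows. No new data are needed.
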